12 STATISTICAL METHODS AND PLANNED ANALYSIS

12.1 General Statistical Considerations

All categorical variables will be summarized by counts and percentages. Descriptive statistics (mean, standard deviation [SD], median, minimum, and maximum) for continuous variables will be utilized. All summaries and analyses conducted will be by treatment cohort (KHK4083 dose levels; combined KHK4083; and placebo) and by visit. The specifics for these outputs will be described in detail within the Statistical Analysis Plan (SAP). The last pre-administration observation will be used as the Baseline value for calculating post-administration changes from Baseline. For efficacy assessments, Baseline is defined as Week 0. Data obtained and entered into the database will be provided in separate data listings showing individual subject values. The planning and reporting of statistical analysis will be carried out as described in the Sponsor's work instructions and standard operating procedures (SOPs) governing clinical studies.

12.2 Populations to be Analyzed

The following analysis sets will be used in the study:

- **Safety Analysis Set:** Includes all subjects who received any (even a partial dose) investigational product (KHK4083 or placebo);
- **Full Analysis Set (FAS):** Includes all subjects who receive at least one full dose of investigational product and who have Baseline data and at least one post-treatment assessment of the primary efficacy variable.

Major protocol deviations will be assessed through the study team's review and the handling of these deviations described in the SAP.

12.2.1 Subject Disposition

The number of subjects enrolled and completed/discontinued for each of the periods (Screening, Induction Therapy, Induction Therapy Follow-up Period, OLE/LTE Therapy, and LTE Therapy Follow-up Period) will be presented. A summary of reasons for discontinuation will be provided. The number of subjects in the Safety Analysis Set and FAS will be provided as well as the number of subjects who were excluded from each analysis set. The reasons why subjects were excluded from any analysis set will be summarized and listed individually.

12.2.2 Demographic and Baseline Disease Characteristics

Summaries will include demographics (including age, race, ethnicity, and sex), height, body weight, and Baseline values for UC assessment in the Safety Analysis Set. All demographic data, including medical/surgical history and physical examination results of note, will be listed by subject.

12.2.3 Prior and Concomitant Medications

The *World Health Organization Drug Dictionary* will be used to classify prior and concomitant medications by Therapeutic Class and Preferred Term. Prior medications include any previous biologic treatment (for any indication), all treatment for UC taken within 6 months prior to Screening, and any other previous medication taken within 1 month prior to Screening. Concomitant medications include medications that started at any time and were taken at any time during the study including the follow-up period. Probiotic usage is to be tracked during the study.

Prior and concomitant medications will be summarized separately in the Safety Analysis Set.

12.2.4 Investigational Product Exposure and Compliance

Extent of exposure for each subject will be calculated as total amount of investigational product administered for the entire Treatment Period. Extent of exposure and total number of doses administered for each treatment during Induction Therapy and OLE/LTE Therapy will be summarized as well as the number of doses administered to subjects by period.

12.3 Efficacy Analysis

All efficacy analyses will be performed in the FAS unless otherwise specified.

12.3.1 Primary Efficacy Analysis

The primary efficacy variable is the change from Baseline (Week 0) in mucosal score presented by the mMES at Week 12 for subjects who received the recommended dose during Induction Therapy. This includes Part A subjects who received the recommended dose identified for Part B as well as the subjects who received the recommended dose during Part B of Induction Therapy. (*Note: For all other subjects who receive KHK4083 at dose levels different than the recommended dose in Parts A and B of Induction Therapy, this efficacy variable will be considered the main secondary variable.*) The primary variable will be used for an exploratory efficacy analysis using a linear model with Baseline values as a covariate to estimate the difference between treatment cohorts (each KHK4083 dose level versus placebo).

In order to test for optimal dose levels within this fitted linear model, three types of contrasts will be defined to demonstrate which KHK4083 dose level is deemed closest to optimal. The first contrast is for the scenario of “10 mg/kg is closest to optimal” and its vector, (P L M H), is (-1 -1 -1 3), where P: Placebo; L: 1.0 mg/kg; M: 3.0 mg/kg; and H: 10 kg/mg. The second contrast is for the scenario of “3.0 mg/kg is closest to optimal” and its vector is (-1 -1 1 1). The third contrast is for the scenario of “1.0 mg/kg is closest to optimal” and its vector is (-3 1 1 1). Each contrast will be tested within the fitted model to determine the dose level providing optimum benefit over placebo.

12.3.2 Secondary Efficacy Analyses

The secondary efficacy variables for all subjects (i.e., recommended dose or any other dose level in Parts A and B of Induction Therapy) are as follows:

- The percentages of subjects with at least a 1-point improvement in their mMES from Baseline (Week 0) to Week 12.
- The percentages of subjects with at least a 1-point improvement in their modified Baron endoscopic score from Baseline (Week 0) to Week 12.
- The mean change in UCEIS (0 to 8) and subscores from Baseline (Week 0) to Week 12.
- The percentage of subjects with a mucosal healing (the mMES \leq 1) at Week 12.
- The change from Baseline (Week 0) in total Mayo Clinic score (0 to 12) at Week 12.
- The change from Baseline (Week 0) in partial Mayo Clinic scores (0 to 9; without sigmoidoscopy) at Weeks 2, 4, 6, 8, 10, and 12.

- The percentages of clinical response (the change from Baseline in the total Mayo Clinic score ≤ -3 and the percentage change from Baseline in the total Mayo Clinic score $\leq -30\%$ to Week 12, with an accompanying decrease in the rectal bleeding subscore of at least 1 point or an absolute rectal bleeding subscore of ≤ 1).
- The percentages of clinical remission (a total Mayo Clinic score ≤ 2 and no subscores > 1) at Week 12.

Treatment (each KHK4083 dose level versus placebo) comparisons by cohort will be performed with the linear model for all secondary efficacy analyses of continuous variables.

12.3.3 Exploratory Efficacy Analysis

Clinical improvement (changes from Baseline [Week 0] to Week 52 in the total Mayo Clinic score) at Week 52 will be summarized. In addition, change from Baseline (Week 0) in partial Mayo Clinic scores (without sigmoidoscopy) will be summarized by study visit at Weeks 16, 20, 24, 28, 32, 36, 40, 44, 48, and 52 and at OLE/LTE Therapy Follow-up Period visits (Weeks 56, 60, and 64).

Clinical response at Week 52 will be summarized. Clinical remission will be summarized at Week 52.

At Weeks 12 and 52, durable clinical response and durable clinical remission (present at both Weeks 12 and 52), and glucocorticoid-free clinical remission at Week 52 will be summarized.

Remission (mMES of 0 or 1, stool frequency subscore of 0 or 1 and rectal bleeding subscore of 0) rates at Weeks 12 and 52 will be summarized.

The percentage of subjects with mucosal healing at Week 52 will be summarized. The percentages of subjects with improvement in the mucosa (change from Baseline of at least a 1-point improvement in the mMES and/or in the modified Baron endoscopic scores; and/or mean change from Baseline in the UCEIS score) at Week 52.

The change from Baseline in HRQL based on IBDQ will be analyzed for total score and 4 subscale scores at all study visits (Weeks 2 to 52, including Induction Therapy Follow-up Period visits (Weeks 16, 20, and 26) and LTE Therapy Follow-up Period visits (Weeks 56, 60, and 64).

At Weeks 16 through 52 and through the OLE/LTE Therapy Follow-up Period (Week 56 through Week 64), the change from Baseline in corticosteroid (glucocorticoid) dosages and the duration of glucocorticoid-free treatment will be summarized.

Treatment (each KHK4083 dose level versus placebo) comparisons by cohort and OLE/LTE will be performed with the linear model for all exploratory efficacy analyses of continuous variables.

Exploratory analyses are described in detail in the SAP.

12.3.4 Sample Size Determination

Assuming a 15% dropout rate, it is anticipated that approximately 60 subjects will be required to be randomized in order to achieve 51 evaluable subjects in the FAS. In Part A (Cohorts 1 - 3), the sample size is based on the feasibility of the safety and tolerability assessment to recommend starting the treatment of the next cohort of 12 subjects/cohort (9 subjects to receive KHK4083 and 3 subjects to receive placebo). In Part B (Cohort 4) for the treatment of 24 subjects (18 subjects to receive KHK4083 at the recommended dose based on the safety and tolerability in Part A and 6 subjects to receive placebo), the sample size is based on the feasibility of exploratory assessments in efficacy and safety at the recommended dose level. Based on the UCEIS and Mayo Clinic scores and from combining Part A and Part B, it is planned to have approximately a total of 27 randomized subjects receive the recommended dose of KHK4083 and 15 subjects receive placebo.

12.3.5 Significance Level

All statistical analyses in this Phase 2 study will be descriptive or exploratory, and no adjustment to control Type I error will be performed.

12.4 Pharmacokinetic, Pharmacodynamic, and Immunogenicity Analyses

12.4.1 Pharmacokinetic Analyses

All subjects with sufficient quantifiable data will be included in the PK analysis. Serum concentration data will be summarized with descriptive statistics at each scheduled time point. Individual serum concentrations at each sampling time point for KHK4083 will be presented by listings. Descriptive summary statistics of serum concentrations including means, ranges, SD, and percent coefficient of variation (%CV) will be presented. Individual and mean concentrations versus time will be plotted on linear and semi-logarithmic scales.

Concentration-time data for Cohorts 1 - 3 (Induction Therapy - Part A and LTE Therapy) will be analyzed individually by non-compartmental analysis methods using actual elapsed times relative to the last dosing. The following PK parameters will be summarized: C_{max} , t_{max} , C_{min} , AUC_{0-t} , $AUC_{0-\tau}$, $AUC_{0-\infty}$, $t_{1/2}$, CLs , V_{ss} , V_z , and R_{ac} . The PK parameters for KHK4083 will be

summarized by dose level and Treatment Period (i.e., Induction Therapy and LTE Therapy). All PK parameters will be summarized using descriptive statistics (mean, SD, maximum, median, minimum, and %CV).

A sparse PK sampling strategy was planned for Cohort 4 (Induction Therapy - Part B and LTE Therapy), therefore population PK analysis using mixed-effect modeling will be applied to the data from both Cohorts 1 - 3 (Part A) and Cohort 4 (Part B). The PK exposure parameters will be calculated using a final population PK model.

The dose proportionality of KHK4083 PK exposure parameters will be assessed using the Power Model for Cohorts 1 - 3 (Induction Therapy - Part A and OLE/LTE Therapy). The PK exposure parameters include C_{max} , AUC_{0-t} , and $AUC_{0-\infty}$, as appropriate. The PK-PD relationships will be explored using graphic tools or modeling as needed.

Additional details of the PK and PK-PD analyses will be addressed in a separate PK-PD Analysis Plan.

12.4.2 Pharmacodynamic Analyses

The PD parameters will be determined in subjects with moderately active UC and summarized by dose level and Treatment Period (i.e., Induction Therapy - Part A and Part B, and OLE/LTE Therapy). For the delayed-type hypersensitivity assay, values will be summarized at Screening and Week 10 for selected investigative sites. For fecal calprotectin, mean change and mean percentage change from Baseline (Week 0) at Week 12 and median values at Weeks 2, 12, and 52 will be analyzed for subjects who received the recommended dose. For the wr-CRP assays, mean change and mean percentage change from Baseline (Week 0) at Week 12 and median values at Weeks 2 through 12 and at Weeks 24, 36, 52, and 64 will be analyzed for the subjects who received the recommended dose. The details will be described in the PK-PD Analysis Plan.

12.4.3 Immunogenicity Analyses

The immunogenicity of KHK4083 will be determined in subjects with moderately active UC. The percentage of subjects with confirmed anti-KHK4083 antibodies will be summarized by dose level and Treatment Period (i.e., Induction Therapy - Part A and Part B, and OLE/LTE Therapy), visit (week), and overall. The effect of positive anti-KHK4083 antibodies on the PK, and possibly efficacy and safety, will be explored.

12.5 Analyses of Safety Data

The overall safety and tolerability of KHK4083 compared to placebo administered in multiple IV doses will be determined for reported AEs (including SAEs), physical examinations, vital signs, body weight, 12-lead ECGs, and clinical laboratory tests. All summaries will be prepared for the Safety Analysis Set.

All subjects will be assessed from the signing of the ICF until 16 weeks after the last dose for potential AEs. Treatment-emergent adverse events (TEAEs) will be grouped and tabulated by MedDRA Preferred Terms (PT) and SOC. All TEAEs will be summarized showing the number and percentage of subjects for each event with a start time within the Treatment Period (i.e., Induction Therapy and OLE or LTE Therapy) and by cohort (KHK4083 versus placebo) during Induction Therapy or KHK4083 dose level versus placebo during OLE/LTE Therapy.

Secondary safety variables in each cohort (Induction Therapy) or KHK4083 dose level (LTE Therapy) will be:

- Serum chemistry, hematology, coagulation profile, and urinalysis parameters;
- Vital signs (systolic and diastolic blood pressure, radial pulse rate, and respiration rate);
- Incidence of abnormal 12-lead ECG findings.

Subject listings, summary tables, and figures including the change over time and shift tables will be generated for vital signs (including body temperature, systolic and diastolic blood pressure, radial pulse rate, and respiratory rate), 12-lead ECGs, body weight, and clinical laboratory assessments (serum chemistry, hematology, coagulation profile, and urinalysis). The results from physical examination will be presented in the subject data listings.

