10.6.3.1 Investigative Site Responsibilities

The Investigator is responsible for evaluating the ECG interpretation in relationship to clinical signs and symptoms and reaching a medical decision regarding the subject's medical status. The ECG findings should be assessed by the Investigator as normal, abnormal not clinically significant, or abnormal clinically significant, as appropriate. All abnormalities, whether assessed as clinically significant or not, will be recorded. The ECG tracing should be initialed and dated by the Investigator.

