8.4 ECGs

Electrocardiogram measurements include heart rate (beats/min), RR interval (msec), PR interval (msec), QRS duration (msec), QT interval (msec), QTc interval (msec) and ECG interpretation. A standard 12-lead ECG will be performed at Screening; during Induction Therapy (predose and at the end of infusion) on Day 1 (Baseline, Week 0), Week 8, and Week 10 and at Week 52 of OLE/LTE Therapy Period. The ECGs will be recorded after the subject has rested for approximately 5 minutes in a supine position.

	Forms			
	Title	Statistical Analysis Plan Template		
	Code	Version	Effective Date	Page
	FRM_ST03_032	01	23 Apr 2015	36 of 53

Summary statistics for the actual ECG parameter values and change from baseline will be provided for each visit. The number and percentage of subjects with elevated QTcF values (> 450 msec, > 480 msec, and > 500 msec) at each scheduled visit (time point) and overall for all post-baseline visits will be presented by treatments (each KHK4083 dose level versus placebo). In addition, the number and percentage of subjects with QTcF values that increase by > 30 msec and > 60 msec from baseline will be presented by treatments at each scheduled visit (time point) and overall for all post-baseline visits. QTcF will be calculated by the Fridericia formula that “(QTcF = QT/(RR)^{1/3})”.

A shift table from baseline to the worst post-baseline values during the treatment period will be provided for QTcF interval. Both scheduled and unscheduled visits during the treatment period will be considered. The following categories will be used: ≤ 450 msec, > 450 and ≤ 480 msec, > 480 and ≤ 500 msec, and > 500 msec.

The numbers and percentages of subjects with reported ‘Abnormal, Clinically Significant Change’ ECG results will be also summarized for each visit by treatments (Placebo, 1.0 mg/kg, 3.0 mg/kg, and 10 mg/kg) and treatment periods (“Double-Blind Therapy Period and Double-Blind Therapy Follow-up Period” and “OLE Therapy Period and OLE Therapy Follow-up Period”).

All ECG parameters will be presented in data listings.

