Listing 16.2.8-5	Clinical Laboratory Values-Urinalysis / Randomized Subjects
Listing 16.2.8-6	Clinical Abnormal Laboratory Values / Randomized Subjects
Listing 16.2.8-7	12-Lead Ecg - Quantitative Data / Randomized Subjects

	Forms			
	Title	Statistical Analysis Plan Template		
	Code	Version	Effective Date	Page
	FRM_ST03_032	01	23 Apr 2015	53 of 53

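### Apart from QTcF outliers, the SAP summarises ECG interpretation only as clinically significant change by visit, so the per-subject incidence of abnormal ECG findings named in protocol 12.5 is not planned

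*Protocol*

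**What the plan says.** Protocol 12.5 introduces a list with "Secondary safety variables in each cohort (Induction Therapy) or KHK4083 dose level (LTE Therapy) will be"; its last entry is "Incidence of abnormal 12-lead ECG findings". Neither the entry nor its lead-in limits it to clinically significant findings. Protocol 10.6.3.1 sets three grades, two of them abnormal: "The ECG findings should be assessed by the Investigator as normal, abnormal not clinically significant, or abnormal clinically significant, as appropriate". It adds: "All abnormalities, whether assessed as clinically significant or not, will be recorded".

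SAP 8.4 takes one count from the interpretation: "The numbers and percentages of subjects with reported ‘Abnormal, Clinically Significant Change’ ECG results will be also summarized for each visit by treatments", split by treatment period. It treats QTcF more fully. Subjects above 450, 480 and 500 msec are counted "at each scheduled visit (time point) and overall for all post-baseline visits will be presented by treatments (each KHK4083 dose level versus placebo"), and increases above 30 and 60 msec are handled the same way. A shift table to the worst post-baseline QTcF also takes in unscheduled visits.

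The ten ECG tables indexed in SAP 9.4 (14.3.4-3.1 to 14.3.4-3.10) are titled for ECG parameters or QTcF. The one ECG listing in SAP 9.6, Listing 16.2.8-7, is titled "12-Lead Ecg - Quantitative Data / Randomized Subjects". SAP 4.5, which records changes to the planned analysis, does not mention this variable.

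**The concern.** The protocol separates an abnormal ECG from a clinically significant one, and section 12.5 uses the wider term. The SAP's count from the interpretation uses the narrower one, and gives no total of subjects affected at any time after baseline. A programmer who follows the SAP exactly produces no by-dose count of subjects with any abnormal interpretation.

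What would be lost is specific. Protocol 10.6.3.2 makes central ECG reading ad hoc, so the site interpretation is the only routine qualitative reading. QTcF thresholds do not capture rhythm, conduction or ST-T findings. Exclusion criterion 11 in protocol 7.3 keeps out subjects with a clinically significant ECG abnormality at Screening, so entrants should be normal or abnormal not clinically significant. A move from normal to abnormal not clinically significant is therefore a change worth seeing by dose, and no summary shows it.

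**Working it through.** The documents give no sample size, power or expected rate for ECG findings, so there is no stated figure to reproduce. The check sets text against text, with two small calculations.

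**1. What is named and what is planned**

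| Element | Protocol 12.5 and 10.6.3.1 | SAP 8.4, interpretation | SAP 8.4, QTcF |
|---|---|---|---|
| Finding | any abnormal | clinically significant only | threshold values and increases |
| Unit | incidence per cohort or dose level | subjects at each visit | subjects at each visit and overall |
| Unscheduled ECGs | not addressed | excluded by the general rule in SAP 4.1 | included in the worst-value shift |
| Table title in SAP 9.4 | not applicable | none | yes |

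The SAP itself separates a by-visit count from an overall one, since it asks for both with QTcF and for only the first with interpretation.

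**2. By-visit counts do not fix an incidence**

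Inputs: planned group sizes from protocol 12.3.4 (9 per active dose in Part A, 15 placebo, 27 at the recommended dose), and the three induction weeks with on-treatment ECGs in protocol 10.6.3 (Weeks 0, 8 and 10, each with an end-of-infusion reading). Assume that all n subjects are read at each visit and that one is clinically significant at each.

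With per-visit counts x_i, the number of subjects affected at least once lies between max(x_i) and min(sum of x_i, n). For x = (1, 1, 1), that is 1 to 3 subjects:

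- n = 27: 1/27 = 3.7% to 3/27 = 11.1%
- n = 15: 1/15 = 6.7% to 3/15 = 20.0%
- n = 9: 1/9 = 11.1% to 3/9 = 33.3%

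The same by-visit display fits a threefold range of incidence, even for the grade that the SAP does count.

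**3. What restricting to clinically significant findings could do**

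This part is illustrative only. Assume that 10% to 20% of subjects develop any new abnormality and 1% to 2% one graded clinically significant. These rates are not in the documents. For n = 27, the expected number is 27p and the chance of seeing none is (1 − p)^27:

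| p | Expected subjects | Chance of none |
|---|---|---|
| 0.01 | 0.27 | 0.762 |
| 0.02 | 0.54 | 0.580 |
| 0.10 | 2.7 | 0.058 |
| 0.20 | 5.4 | 0.002 |

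On these assumptions the clinically significant count is empty with probability 58% to 76%, against 0.2% to 6% for any abnormality. This is not the chance that the report shows no ECG abnormality, because the QTcF counts are separate.

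**The case against.** The strongest reply is that the SAP already reports ECG abnormality well. The QTcF counts are per subject, by dose, overall after baseline and independent of investigator judgement. Protocol 12.1 calls for summaries by visit and leaves output detail to the SAP. Section 12.5 defines neither incidence nor abnormal. Protocol 10.6.8 requires clinically important ECG changes to be collected, and those reported as adverse events enter the treatment-emergent tables. What remains is abnormality graded not clinically significant and outside the QTcF criteria, the least consequential class.

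Much of this stands, and it rules out several stronger readings that a reader might infer:

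- **That abnormal ECGs go unreported, or that no incidence is produced.** The overall QTcF counts contradict this.
- **That a by-visit display breaches the protocol.** Section 12.1 asks for one. The shortfall is the missing total beside it.
- **That the interpretation will not be listed.** SAP 8.4 names ECG interpretation among the measurements and commits to listing all ECG parameters, and SAP 4.1 promises listings of all eCRF data. Only the listing's title is out of step.
- **That the protocol demands a shift table of interpretation.** Its call for ECG shift tables can be met by the QTcF shift.
- **That the titles in SAP 9.4 prove what the tables contain.** The shells are in a separate document (SAP 9.7), so the contents of the ECG parameter tables cannot be checked.

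None of this supplies a per-subject, by-dose count of any abnormal interpretation. QTcF does not stand in for rhythm, conduction or ST-T findings, and the adverse event route covers only what is judged clinically important.

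**Conclusion.** The point holds in a limited form. For everything outside QTcF, the SAP is narrower than the variable named in protocol 12.5 in two ways: it drops the not clinically significant grade, and it gives visit counts without a per-subject total. SAP 4.5 does not say that this was intended.

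This is a modest gap in descriptive safety reporting. It touches no efficacy analysis, and protocol 12.3.5 makes all analyses descriptive or exploratory. The three-to-one range in the by-visit illustration follows from arithmetic on assumed counts. The 10% to 20% and 1% to 2% rates are assumptions without a source in the documents and show direction only. The conclusion rests on the SAP text and table titles and would weaken if the shells already include an any-abnormal total.

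**What to change.** In SAP 8.4 and 9.4, add one table of the number and percentage of subjects with at least one post-baseline abnormal ECG interpretation that was not present at baseline. Give two rows, any abnormal and clinically significant. Include unscheduled ECGs, stated as an exception to the SAP 4.1 rule. Show dose levels, combined KHK4083 and placebo, for each treatment period (Induction, LTE, OLE). State the denominator and the new-from-baseline rule, since the protocol defines neither. Footnote that in the OLE the placebo column holds subjects randomised to placebo who then receive KHK4083, as note 3 to SAP Table 2 says.

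A shift table of interpretation from baseline to worst post-baseline grade is optional. Listing 16.2.8-7 needs only a title that matches the SAP 8.4 text. If the narrowing was deliberate, the alternative is to declare and justify it in SAP 4.5.

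The cost is SAP wording and one extra descriptive table from data already collected, with no new procedure.
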